7.9 DATA ANALYSIS

7.9.1 MAIN ANALYSIS

For the base cohort, patient characteristics at baseline will be described using standard descriptive statistics. The unmatched study cohort, which will also address the tertiary objective, will be used to provide and compare baseline patient characteristics between the two groups. These comparisons will also be provided for the matched cohort.

For the analysis of the primary objective, the matched cohort will be used to estimate the crude 1-year cumulative incidence of severe and moderate COPD exacerbations for the two combination treatment groups. The main comparative analysis will also be based on the matched cohort and a time-dependent Cox proportional hazard regression model to perform an as-treated analysis that assesses the effect of current use of LABA-TIO combination versus the LABA-ICS combination on the risk of a first COPD exacerbation. It will provide an estimate of the hazard ratio (HR) of a COPD exacerbation associated with LABA-TIO use relative to LABA-ICS use, along with 95% confidence intervals (CI). Current use will be defined as a prescription dispensed within the 60-day period of the date defined by the risk set of the Cox model. This approach allows consideration of exposure as time-dependent, accounting for the changes in exposure during the follow-up. In particular, this analysis

censors patients stopping one or both of the drugs prior to the index date. Besides the matching inherent in the design, the Cox proportional hazard regression model will be adjusted for additional confounders. This model will include patient characteristics found to be different after matching on propensity scores, as well as the decile of propensity score. Body mass index (BMI) is expected to be the only variable with missing data in the CPRD, though infrequently (less than 4% of subjects in our previous studies in COPD). Patients with missing BMI will be classified as a separate category.

The analysis of the secondary objective related to the rate of exacerbation will be based on the negative binomial regression models, which corresponds to a Poisson regression model adjusted for between-subject variation in exacerbations, with the same approach to covariate adjustment as the primary analysis. A 30-day gap between events will be used to distinguish between one continuous exacerbation and two separate events. The analysis of the secondary objective related to the risk of pneumonia will use a time-dependent Cox proportional hazard regression model with an as-treated approach, similar to that of the primary analysis.

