7.4.3 COVARIATES

Sex, previous treatment and previous acute COPD exacerbation, as well as calendar year of cohort entry, are all matching factors and will thus inherently be accounted for.

Although we will use the high-dimensional approach to identify variables entering the time-conditional propensity score, some key covariates will be highlighted. First, we will identify key lifestyle variables available in the CPRD, known to be risk factors and potential confounders, including the body mass index (BMI), smoking status and excessive alcohol consumption. Missing data for smoking status and BMI will be entered as an additional category in the model. We will also explore the possibility of obtaining blood eosinophils measured in the year prior to cohort entry and will use this information only if complete.

Second, the occurrence of the study outcomes prior to cohort entry will be identified during the one-year baseline period and adjusted for in the analysis if found to be imbalanced between treatment groups after propensity score matching. In particular, COPD exacerbations occurring in the 30 days prior to the study cohort entry date, a marker of COPD exacerbation risk, will be identified separately from those occurring previously during the baseline year. In addition, the severe exacerbations requiring hospitalizations will be counted, while the moderate exacerbations will be identified from counts of prescriptions for oral corticosteroids.

Third, use of other respiratory drugs during the baseline period will be included as a measure of COPD severity. Thus, the number of prescriptions for short-acting beta-agonists, anticholinergics, methylxanthines and muscarinic antagonists used during the year prior to cohort entry will be identified. As well, the number of prescriptions for antibiotics for a respiratory condition will be counted. In addition, we will count the number of prescriptions for the study drugs used during the baseline period. These will be combined into a single variable because of the study design which inherently selects patients into the two study groups according to their prior LABA, TIO or ICS use. Finally, for each of the cohorts, baseline co-morbidity will be measured using diagnoses and prescriptions for various conditions observed often in patients with COPD, namely cardiovascular disease, diabetes, thyroid disease, renal failure, autoimmune disease and cancer, all in the year prior to cohort entry.

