7.6 BIAS

Several potential biases inherent to any observational study need to be considered. First, confounding by indication could be an issue. Matching subjects initiating LABA-TIO with subjects initiating LABA-ICS on several marker of disease, including prior COPD exacerbations, previous treatment and on the propensity score should limit this potential bias since matched subjects will have comparable probability of using either combination. In addition to matching on the propensity score, sex, prior exacerbation, prior treatment and calendar time, several variables such as general severity of COPD, comorbidity and concomitant drug use will be in the propensity score and adjusted for in the outcome model. Second, there is the possibility of information bias due to misclassification of the outcomes or exposure. CPRD contains prescriptions written by the GP rather than filled or taken by patients. This could be a source of misclassification of exposure. Another source of information bias due to the presence of hospitalizations during follow-up, particularly during the current exposure window, where GP prescriptions are not available, so that exposure is not measurable. Finally, the linkage to HES data to identify hospitalization for COPD exacerbation and for community-acquired pneumonia should reduce the potential for misclassification of outcomes.

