7.7 STUDY SIZE

In our previous study of the cardiovascular effects of long-acting bronchodilators, there were around 230,000 users of LABA or TIO between 2002 and 2012 in the CPRD, which should include around 140,000 who come from HES-linked practices [P16-10095]. From these, we expect around 4,000 who received a LABA and tiotropium on the same day, where the LABA is not combined with an inhaled corticosteroid in a single inhaler. The number of users of LABA-ICS is over 100,000, providing a large pool for matching purposes. Thus, after matching and trimming, we expect the study to include a minimum of 3,000 patients per arm, a conservative estimate. Using recent data from the FLAME trial [P16-05628], we expect that the cumulative incidence of a first COPD exacerbation, moderate or severe,

during the one-year follow-up is expected to be 50%. These sample sizes will permit to detect a 15% reduction in the risk of a first exacerbation (hazard ratio 0.85) with 99% power and a 10% reduction (hazard ratio 0.90) with 97% power. For the severe exacerbations, we expect the one-year cumulative incidence to be around 15%, which will permit to detect a 20% reduction in the risk of a first severe exacerbation (hazard ratio 0.80) with 92% power.

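### Beyond the propensity score decile, the primary Cox model adjusts only for characteristics found imbalanced after matching, with no criterion given and against Section 7.6; a fixed covariate set should be prespecified.

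*Combined protocol and SAP*

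**What the plan says.** Three sections of the combined protocol and SAP describe adjustment in the outcome model.

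- **Section 7.9.1 (Main analysis):** "This model will include patient characteristics found to be different after matching on propensity scores". The same sentence also puts the propensity score decile in the model, always. Later in 7.9.1, the negative binomial model for the exacerbation rate takes the same covariate approach.
- **Section 7.4.3 (Covariates):** prior occurrences of the study outcomes will be "adjusted for in the analysis if found to be imbalanced between treatment groups after propensity score matching".
- **Section 7.6 (Bias):** several variables, among them general COPD severity, "comorbidity and concomitant drug use will be in the propensity score and adjusted for in the outcome model". No condition is attached.

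On what the design already controls, 7.4.3 states: "Sex, previous treatment and previous acute COPD exacerbation, as well as calendar year of cohort entry, are all matching factors". Section 7.3 shows that the exacerbation factor is presence or absence in the prior year. It also allows the closest available subject to be taken when no tight score match exists, with adjustment for the score.

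**The concern.** A statistician following 7.6 would put severity, comorbidity and drug use in the Cox model in every case. One following 7.9.1 and 7.4.3 would include them only if they looked imbalanced, and would have to invent the criterion, since neither a standardised difference nor a test is named. The two could fit different primary models to the same matched cohort.

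The conditional rule can also leave out strong predictors. Matching fixes only whether there was an exacerbation in the prior year. The number of exacerbations and their recency within 30 days are not exactly matched, although 7.4.3 itself treats recency as a marker of risk. Age appears as an eligibility limit but is neither a matching factor nor a listed covariate. A modest imbalance in a strong predictor that passes unremarked stays in the hazard ratio. What is at stake is how well the primary estimate is prespecified, and a bias that could be a noticeable part of the smaller effect the study is sized for.

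**Working it through.** **Inputs from Section 7.7.** Size: "after matching and trimming, we expect the study to include a minimum of 3,000 patients per arm, a conservative estimate". The one-year incidence of a first exacerbation "during the one-year follow-up is expected to be 50" per cent. If that applies to both arms, there are 0.50 × 6,000 = 3,000 events. For the larger effect, the plan says it can "detect a 15% reduction in the risk of a first exacerbation (hazard ratio 0.85) with 99% power". For the smaller effect, its figure is "a 10% reduction (hazard ratio 0.90) with 97% power". Alpha is not stated; two-sided 0.05 is assumed.

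**The plan's own power figures.**
- Read as risk ratios (50% against 42.5%, and 50% against 45%), a two-proportion test with 3,000 per arm gives 99.99% and 97.3%. For the second: 0.05 / √[(0.25 + 0.2475)/3,000] = 3.88, and Φ(3.88 − 1.96) = 97.3%. This reproduces the plan.
- Read as hazard ratios with 3,000 events, Schoenfeld's formula Φ(|ln HR| × √3,000 / 2 − 1.96) gives 99.4% at 0.85 and 82.3% at 0.90.

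The mismatch at 0.90 is a separate matter. It is noted because the simulated powers below start from about 82%, not 97%. Section 7.7 does not rely on covariate adjustment for power.

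**Bias from an imbalance outside the score.** The documents give no prognostic strengths, so these are assumed. For a covariate with log-hazard β per SD and standardised difference d between arms, the hazard ratio is multiplied by roughly exp(−βd) when the lower-risk arm is LABA-TIO, and by exp(+βd) when it is LABA-ICS. The null case was simulated with 3,000 per arm, about 50% events, a tight score match, the score decile in the Cox model, a covariate correlated 0.5 with the score, and 300 replicates per cell.

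| β per SD | d | exp(−βd) | Simulated HR, decile only | Type I error |
|---|---|---|---|---|
| 0.4 | 0.05 | 0.980 | 0.98 | 8% |
| 0.4 | 0.09 | 0.965 | 0.97 | 14% |
| 0.6 | 0.05 | 0.970 | 0.97 | 10% |
| 0.6 | 0.09 | 0.947 | 0.95 | 24% |

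Adding the covariate returned a hazard ratio of 1.00 and a type I error of 4 to 6% in every cell. On the log scale, βd runs from 0.020 to 0.054. The 10% target is |ln 0.90| = 0.105, so the bias is about 19% to 51% of it.

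**A single weaker binary covariate.** With prevalence p, covariate hazard ratio h and prevalences p ± d√[p(1−p)]/2 in the two arms, the bias factor is [1 + p₁(h−1)] / [1 + p₀(h−1)].
- p = 0.2, d = 0.05, h = 1.5: 1.105/1.095 = 1.009.
- p = 0.2, d = 0.10, h = 2.0: 1.22/1.18 = 1.034.

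This is about 1 to 3%, before the decile removes any of it.

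**Imbalance carried by the score (loose matches).** Over the same ranges of β and d, omitting the decile gave hazard ratios of 0.95 to 0.98. With the decile they returned to 1.00, with type I error of 4 to 5%.

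**Power with balanced arms and a true conditional HR of 0.90.** The score was correlated 0.5 with prognosis; 1,000 replicates per row; Monte Carlo error about 1.3 points.

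| Prognostic SD (log-hazard) | Score only: power (HR) | Full adjustment: power |
|---|---|---|
| 0.3 | 80% (0.903) | 81% |
| 0.5 | 76% (0.905) | 81% |
| 0.8 | 68% (0.913) | 80% |

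The gain is about 1, 5 and 11 points. At HR 0.85 (400 replicates), power was 98%, 98% and 95% with no adjustment at all, against about 99% with full adjustment.

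**The case against.** The strongest defence is that the score decile is always in the model and that the variables named in 7.6 enter the score. On a lenient reading, 7.6 means adjustment through the score, and the conflict is one of wording. The rule also looks at baseline balance and not at outcomes, so it does not select covariates on the treatment effect. Both observations are fair. The second stands fully. The first stands for imbalance the score carries, where the decile works. It does not help with imbalance outside the score, and it does not supply the missing criterion.

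Four stronger readings are tempting and are not supported:

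- **That the model adjusts for nothing except imbalanced characteristics.** The same sentence of 7.9.1 includes the decile, and several prognostic factors are matched.
- **That type I error is inflated in general to as much as a quarter.** This needs imbalance outside the score that also goes unflagged. With 3,000 per arm, a difference of 0.09 has z = 0.09 × √(3,000/2) = 3.49, which a significance test would flag; a difference of 0.05 has z = 1.94, which a 5% test would just miss. The upper figures therefore presuppose a lenient cut-off such as 0.10, which the plan does not state.
- **That the plan gives up substantial power.** The gain rests on assumed prognostic strengths. It is partly a move from a marginal to a conditional hazard ratio; if 0.90 is the marginal value, the planned model does not lose this power.
- **That age is left out of the score.** Section 7.3 draws on all available data and lists examples, and 7.4.3 only highlights key covariates. Not naming age does not show that it is omitted.

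**Conclusion.** The concern holds in limited form. Section 7.6 and Sections 7.4.3 and 7.9.1 do not agree, no criterion for imbalance is given, and the adjustment set for the primary hazard ratio and the rate model is therefore not fixed in advance.

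The possible bias is about 2 to 5% on the hazard ratio for a strong covariate, and about 1 to 3% for a single weaker binary one. It arises only where the imbalance lies outside the score and is not picked up by whatever criterion is used. These sizes depend on assumed prognostic strengths and assumed residual differences; the documents supply neither. The power argument is secondary: about 1 to 11 points at HR 0.90 and little at 0.85.

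The change is worth making because fixed adjustment removes both the ambiguity and this source of bias for the covariates listed, at almost no cost. The plan as written is not shown to give a seriously wrong answer.

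**What to change.** In 7.9.1, prespecify a fixed adjustment set for the Cox and negative binomial models, included whatever the post-match balance and alongside the score decile:

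- age, smoking, BMI and alcohol;
- counts of moderate and of severe exacerbations, in the baseline year and in the last 30 days;
- respiratory drug and antibiotic prescription counts;
- the comorbidities listed in 7.4.3.

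Name age explicitly as a score variable. Keep the balance table as a diagnostic that can add covariates but not remove them, with a stated threshold. Bring 7.4.3, 7.6 and 7.9.1 into line with this.

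The cost is one paragraph and about 15 to 20 parameters, depending on coding. Even if as-treated censoring cut the 3,000 events to 2,000 (assumed), 20 covariate parameters plus 9 for the deciles leave 2,000/29, or about 69 events per parameter. Apart from age, which the eligibility rule already requires, these are variables that 7.4.3 plans to identify. Section 4 schedules extraction to start on 1 June 2017, after the 19 May 2017 version date, so the change could precede the data. The hazard ratio becomes more explicitly conditional on the covariates, and the report should say so.

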propensity score-matched approach. The potential comparator subjects will be selected from the base cohort by forming time-based exposure sets defined by the calendar year of entry into the base cohort for the LABA-TIO and LABA-ICS simultaneous prescription users. To allow matching on the propensity of treatment choice, we will compute high-dimensional time-conditional propensity scores (TCPS) by identifying all available data (e.g., diagnoses, procedures, medications) in the one-year period prior to the date of cohort entry for each time-based exposure set using Cox proportional hazards regression. Then, for each LABA-TIO exposed subject, and starting chronologically with the first one, we will identify a matched comparator subject from the members of the subject's time-based exposure set. We will first match subjects on sex, previous components of the study treatment (LABA only, TIO only, ICS alone, none of these) and the presence of an acute COPD exacerbation in the year before cohort entry. The matched reference subject will then be selected as the one with the closest time-conditional propensity score in the matched set, after trimming within each exposure set, and allowing a maximum difference in scores of 0.05 for a match. In the absence of a tight propensity score match, we will take the closest and the analysis will be complemented by an adjustment for the propensity score.

After matching, the subjects in the study cohort will be followed up for up to one year from cohort entry (the date of the matched set), with follow-up ending at the earliest of the date of a switch or addition of either an ICS for the LABA-TIO group or of tiotropium to the LABA-ICS group, death, one year after cohort entry, December 31, 2016, or the end of coverage in the practice, whichever occurs first.

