4.2.6 Seasonality?				
4.3 Does the protocol define how the study population will be sampled from the source population? (e.g. event or inclusion/exclusion criteria)				16

Comments:

--

Section 5: Exposure definition and measurement	Yes	No	N/A	Page Number(s)
5.1 Does the protocol describe how exposure is defined and measured? (e.g. operational details for defining and categorising exposure)				17
5.2 Does the protocol discuss the validity of exposure measurement? (e.g. precision, accuracy, prospective ascertainment, exposure information recorded before the outcome occurred, use of validation sub-study)				19
5.3 Is exposure classified according to time windows? (e.g. current user, former user, non-use)				17
5.4 Is exposure classified based on biological mechanism of action and taking into account the pharmacokinetics and pharmacodynamics of the drug?				

Section 5: Exposure definition and measurement	Yes	No	N/A	Page Number(s)
5.5 Does the protocol specify whether a dose-dependent or duration-dependent response is measured?				20

Comments:

Section 6: Endpoint definition and measurement	Yes	No	N/A	Page Number(s)
6.1 Does the protocol describe how the endpoints are defined and measured?				17-18
6.2 Does the protocol discuss the validity of endpoint measurement? (e.g. precision, accuracy, sensitivity, specificity, positive predictive value, prospective or retrospective ascertainment, use of validation sub-study)				19

Comments:

Section 7: Confounders and effect modifiers	Yes	No	N/A	Page Number(s)
7.1 Does the protocol address known confounders? (e.g. collection of data on known confounders, methods of controlling for known confounders)				18

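### Calendar time is controlled by year only and no term covers season, so an arm difference in entry month, if there is one, would not be adjusted for in the short as-treated follow-up

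*Combined protocol and SAP*

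**What the plan says.** - **Matching (Section 7.3).** Comparators come from "time-based exposure sets defined by the calendar year of entry into the base cohort". Cohort entry is each subject's own first date of simultaneous prescriptions.
- **Covariates (Section 7.4.3).** "Sex, previous treatment and previous acute COPD exacerbation, as well as calendar year of cohort entry, are all matching factors". This names the year of cohort entry, whereas Section 7.3 names the year of base-cohort entry. A patient may join the base cohort on one drug and start the combination years later, so the two can differ. Section 7.6 says only that calendar time is matched.
- **Model (Section 7.9.1).** "This model will include patient characteristics found to be different after matching on propensity scores, as well as the decile of propensity score". The pneumonia model is described as similar to the primary one.
- **Exposure (Section 7.9.1).** "Current use will be defined as a prescription dispensed within the 60-day period of the date defined by the risk set" of the Cox model. Patients who stop either drug are censored. Follow-up otherwise runs to at most one year.

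Month, quarter and season appear in none of these places.

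**The concern.** COPD exacerbations and pneumonia can be expected to vary with season, although the documents give no seasonal rates. Matching on year, under either reading, allows a patient who starts in January to be paired with one who starts in July. Over a complete year each would pass through every season and the difference would nearly average out. Under the 60-day rule some patients contribute only one season. If the arms differ in the months in which treatment starts, that difference enters the comparison of hazards.

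Section 7.7 aims to detect hazard ratios of 0.90 and 0.85 for first exacerbation, so a shift of a few percent would be a noticeable part of the target effect. The plan does not undertake to tabulate entry month by arm, so an imbalance could go unseen.

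**Working it through.** **The plan's own figure, for scale.** Section 7.7 says "we expect the study to include a minimum of 3,000 patients per arm", with 50% one-year incidence and 97% power for a 10% reduction. Reading that as 50% v 45%, two-sided 5% (assumed from the 95% confidence interval):

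z = [0.05 × √3000 − 1.96 × √(2 × 0.475 × 0.525)] / √(0.50 × 0.50 + 0.45 × 0.55) = (2.739 − 1.384) / 0.705 = 1.92, so power is 97.3%.

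The stated figure reproduces as a ratio of risks and is unaffected by this point. The plan gives no figure for season.

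**Inputs from the documents.** 3,000 per arm; 50% one-year incidence; 60-day window; at most one year of follow-up.

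**Assumptions, because the documents give no figures.**
- The true hazard ratio is 1, and the Cox time axis is time since cohort entry.
- Daily hazard is h(d) = h0 × [1 + A cos(2π(d − 15)/365)], peaking in mid-January, with h0 = −ln(0.5)/365 = 0.0019 and A = (R − 1)/(R + 1). The peak-to-trough ratio R is 2 (range 1.5 to 3), so A = 1/3 at R = 2.
- All patients are on treatment for 60 days, then stop exponentially after a mean of 30 to 120 further days. Allowing for events and the one-year limit, mean follow-up is 83 to 141 days.
- The arms differ in the share entering from October to March. Entry is even within each half-year.

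**Calculation.** For each day t since entry, take the number at risk Y(t) and the expected events E(t) in each arm (1 = LABA-TIO, 0 = LABA-ICS), averaged over entry dates. Solve the Cox score equation for β:

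Σ { E1 − (E1 + E0) × Y1 e^β / (Y1 e^β + Y0) } = 0.

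With D events, the false-positive rate is Φ(z − 1.96) + Φ(−z − 1.96), where z = |β| × √(D/4).

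**Results at R = 2: expected hazard ratio (false-positive rate)**

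| Winter entry, LABA-TIO v LABA-ICS | Mean 83 days, about 940 events | Mean 141 days, about 1,600 events | Full year, 3,000 events |
|---|---|---|---|
| 50% v 50% | 1.000 (5%) | 1.000 (5%) | 1.000 (5%) |
| 45% v 55% | 0.969 (8%) | 0.987 (6%) | 0.998 (5%) |
| 40% v 60% | 0.938 (16%) | 0.975 (8%) | 0.996 (5%) |

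Example, second row at 83 days: β = ln 0.969 = −0.0315; z = 0.0315 × √(940/4) = 0.48; rate = Φ(−1.48) + Φ(−2.44) = 0.07 + 0.007, about 8%.

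If the imbalance is reversed, the ratios invert: 1/0.987 to 1/0.969 is 1.013 to 1.032, and 1/0.975 to 1/0.938 is 1.026 to 1.066.

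Over R = 1.5 to 3 with short follow-up, the 10-point difference gives about 0.95 to 0.99 and the 20-point difference about 0.91 to 0.98.

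On the log scale, the 10-point shift at R = 2 is 0.013/0.105 to 0.0315/0.105, or 12% to 30% of ln 0.90.

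**Second check, with fixed follow-up.** One arm has 52% to 60% of entries in a given half-year and the other 50%; R is 1.5 to 3; the seasonal peak is placed where it does most harm. The hazard ratio moves by 0.5% to 6% if everyone is followed for 60 days and by 0.3% to 4% at 180 days. It moves by at most about 1.5% if half are followed for 60 days and half for 365, and by at most 0.7% at 365 days.

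**Pneumonia.** At an assumed 5% a year, the same second check gives similar shifts at 60 days. Events are few, so the false-positive rate stays at or below 5.7% for every follow-up length tried.

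**The case against.** The strongest reply is that nothing in the documents suggests that entry month differs by arm, and without a difference there is no bias. This stands: seasonal amplitude, imbalance and stopping rate are all assumed above.

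Further points on that side:

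- **Follow-up length.** Sixty days is the shortest course, not the expected one. The abstract gives an expected exposure of one year, which may be a maximum because Section 7.3 says up to one year. If most patients stay on treatment, the bias is negligible. No section supports a mean of 83 to 141 days, and none excludes it.
- **Proxies.** Matching on exacerbation in the prior year, the 30-day exacerbation marker and the high-dimensional score carry some seasonal information and would reduce the bias. The reduction is partial: entry month is not a named input, the marker is adjusted for only if imbalanced, and it describes recent illness, not the season ahead.
- **Adjustment rule.** Section 7.9.1 could admit entry month as a characteristic found to differ, but only if someone tabulates it and treats it as one.
- **Shared date.** Section 7.3 mentions the date of the matched set. Cohort entry is nevertheless defined for each subject, and the sets are formed by year.

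A reader might infer that the 2002 launch of tiotropium creates the imbalance by moving LABA-TIO starts later in the year. It does not produce these figures. Later entry adds October to December starts but removes January to March ones. Under assumed launch dates and linear uptake, the October-to-March share differs by at most 0.06 percentage points and the hazard ratio is 1.002 to 1.003 at R = 2 (at most 1.005 at R = 3).

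A reader might also infer something from the seasonality item in the ENCePP checklist, which shows no answer in the text available. The answer may have been lost in extraction, so the item proves nothing.

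**Conclusion.** The point holds as a conditional one. Control is by year only, no term covers season, and as-treated follow-up can be short enough for season not to average out. If winter entry differs by 10 points, the exacerbation hazard ratio could be off by roughly 1% to 3%; at 20 points, by 3% to 6%. Either direction is possible. These sizes rest on an assumed peak-to-trough ratio of 2 and mean follow-up of 83 to 141 days, before any reduction from the propensity score and prior-exacerbation adjustment. With complete one-year follow-up the shift is under 1%.

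The documents do not support the stronger readings that the primary hazard ratio is biased, or that any seasonal difference passes into it undiminished. They also give no ground for requiring a change to the negative binomial model: Section 7.4.2.2 defines that outcome over the one-year follow-up, and no calculation shows a problem there. This is an inexpensive safeguard in a non-randomised comparison, not a demonstrated error.

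**What to change.** 1. In Section 7.9.1, prespecify calendar quarter (or month) as a time-dependent covariate in the as-treated Cox model for first exacerbation.
2. Prespecify calendar quarter in the pneumonia Cox model, where events are fewer.
3. Tabulate month of cohort entry by arm in the matched cohort.
4. Reconcile Sections 7.3 and 7.4.3 on which calendar year defines the exposure sets.

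The first three need a sentence or two in Section 7.9.1 and one table. The model cost is 3 degrees of freedom for quarter or 11 for month, against about 940 to 1,600 first-exacerbation events under the short follow-up assumed above. The dates are already held. Apart from settling which year defines the sets, the matching need not change.
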